5.3.5.5 Abnormal Vital Sign Values

Not every vital sign abnormality qualifies as an adverse event. A vital sign result must be reported as an adverse event if it meets any of the following criteria:

- Is accompanied by clinical symptoms
- Results in a change in study treatment (e.g., dosage modification, treatment interruption, or treatment discontinuation)
- Results in a medical intervention or a change in concomitant therapy
- Is clinically significant in the investigator's judgment

It is the investigator's responsibility to review all vital sign findings. Medical and scientific judgment should be exercised in deciding whether an isolated vital sign abnormality should be classified as an adverse event.

If a clinically significant vital sign abnormality is a sign of a disease or syndrome (e.g., high blood pressure), only the diagnosis (e.g., hypertension) should be recorded on the Adverse Event eCRF.

Observations of the same clinically significant vital sign abnormality from visit to visit should only be recorded once on the Adverse Event eCRF (see Section 5.3.5.3 for details on recording persistent adverse events).

5.3.5.6 Abnormal Liver Function Tests

The finding of an elevated ALT or AST ($>3 \times$ baseline value) in combination with either an elevated total bilirubin ($>2 \times$ ULN) or clinical jaundice in the absence of cholestasis or other causes of hyperbilirubinemia is considered to be an indicator of severe liver injury (as defined by Hy's Law). Therefore, investigators must report as an adverse event the occurrence of either of the following:

- Treatment-emergent ALT or AST $>3 \times$ baseline value in combination with total bilirubin $>2 \times$ ULN (of which $\geq 35\%$ is direct bilirubin)
- Treatment-emergent ALT or AST $>3 \times$ baseline value in combination with clinical jaundice

The most appropriate diagnosis or (if a diagnosis cannot be established) the abnormal laboratory values should be recorded on the Adverse Event eCRF (see Section 5.3.5.4) and reported to the Sponsor immediately (i.e., no more than 24 hours after learning of the event), either as a serious adverse event or an adverse event of special interest (see Section 5.4.2).

5.3.5.7 Deaths

All deaths that occur during the protocol-specified adverse event reporting period (see Section 5.3.1), regardless of relationship to study drug, must be recorded on the Adverse Event eCRF and immediately reported to the Sponsor (see Section 5.4.2). This includes death attributed to progression of COVID-19.

Death should be considered an outcome and not a distinct event. The event or condition that caused or contributed to the fatal outcome should be recorded as the single medical concept on the Adverse Event eCRF. Generally, only one such event should be reported. If the cause of death is unknown and cannot be ascertained at the time of reporting, "**unexplained death**" should be recorded on the Adverse Event eCRF. If the cause of death later becomes available (e.g., after autopsy), "unexplained death" should be replaced by the established cause of death. The term "**sudden death**" should not be used unless combined with the presumed cause of death (e.g., "sudden cardiac death").

If the death is attributed solely to progression of COVID-19, "coronavirus disease-2019 progression" should be recorded on the Adverse Event eCRF.

Deaths that occur after the adverse event reporting period should be reported as described in Section 5.6.

5.3.5.8 Preexisting Medical Conditions

A preexisting medical condition is one that is present at the screening visit for this study. Such conditions should be recorded on the General Medical History and Baseline Conditions eCRF.

A preexisting medical condition should be recorded as an adverse event only if the frequency, severity, or character of the condition worsens during the study. When recording such events on the Adverse Event eCRF, it is important to convey the concept that the preexisting condition has changed by including applicable descriptors (e.g., "more frequent headaches").

5.3.5.9 Lack of Efficacy or Worsening of COVID-19

Medical occurrences or symptoms of deterioration that are anticipated as part of COVID-19, such as fluctuations in symptoms, should not be recorded as adverse events. However, deterioration that is judged by the investigator to have unexpectedly worsened in severity or frequency or changed in nature at any time during the study should be recorded as an adverse event. When recording an unanticipated worsening of COVID-19 on the Adverse Event eCRF, it is important to convey the concept that the condition has changed by including applicable descriptors (e.g., "accelerated worsening of coronavirus disease 2019").

5.3.5.10 Hospitalization or Prolonged Hospitalization

Any adverse event that results in hospitalization (i.e., inpatient admission to a hospital) or prolonged hospitalization should be documented and reported as a serious adverse event (per the definition of serious adverse event in Section 5.2.2), except as outlined below.

An event that leads to hospitalization under the following circumstances should not be reported as an adverse event or a serious adverse event:

- Hospitalization for a preexisting condition, provided that all of the following criteria are met:

The hospitalization was planned prior to the study or was scheduled during the study when elective surgery became necessary because of the expected normal progression of the disease

The patient has not experienced an adverse event

An event that leads to hospitalization under the following circumstances is not considered to be a serious adverse event, but should be reported as an adverse event instead:

- Hospitalization that was necessary because of patient requirement for outpatient care outside of normal outpatient clinic operating hours

5.3.5.11 Cases of Overdose, Medication Error, Drug Abuse, or Drug Misuse

Overdose (accidental or intentional), medication error, drug abuse, and drug misuse (hereafter collectively referred to as "special situations"), are defined as follows:

- Accidental overdose: accidental administration of a drug in a quantity that is higher than the assigned dose
- Intentional overdose: intentional administration of a drug in a quantity that is higher than the assigned dose
- Medication error: accidental deviation in the administration of a drug

In some cases, a medication error may be intercepted prior to administration of the drug.

- Drug abuse: intentional excessive use of a drug that may lead to addiction or dependence, physical harm, and/or psychological harm
- Drug misuse: intentional deviation in the administration of a drug that does not qualify as drug abuse

In cases where drug is to be self-administered by the patient, drug misuse could involve the drug being administered to someone other than the patient.

Special situations are not in themselves adverse events, but may result in adverse events. Each adverse event associated with a special situation should be recorded separately on the Adverse Event eCRF. If the associated adverse event fulfills seriousness criteria or qualifies as an adverse event of special interest, the event should be reported to the Sponsor immediately (i.e., no more than 24 hours after learning of the event; see Section 5.4.2). For AT-527 (or matching placebo), adverse events associated with special situations should be recorded as described below for each situation:

- Accidental overdose: Enter the adverse event term. Check the "Accidental overdose" and "Medication error" boxes.
- Intentional overdose: Enter the adverse event term. Check the "Intentional overdose" box. If drug abuse is suspected, check the "Drug abuse" box. If drug abuse is not suspected, check the "Drug misuse" box.
- Medication error that does not qualify as an overdose: Enter the adverse event term. Check the "Medication error" box.
- Medication error that qualifies as an overdose: Enter the adverse event term. Check the "Accidental overdose" and "Medication error" boxes.

- Drug abuse that does not qualify as an overdose: Enter the adverse event term. Check the "Drug abuse" box.
- Drug abuse that qualifies as an overdose: Enter the adverse event term. Check the "Intentional overdose" and "Drug abuse" boxes.
- Drug misuse that does not qualify as an overdose: Enter the adverse event term. Check the "Drug misuse" box.
- Drug misuse that qualifies as an overdose: Enter the adverse event term. Check the "Intentional overdose" and "Drug misuse" boxes.

In addition, all special situations associated with AT-527 (or matching placebo), regardless of whether they result in an adverse event, should be recorded on the Adverse Event eCRF as described below:

- Accidental overdose: Enter the drug name and "accidental overdose" as the event term. Check the "Accidental overdose" and "Medication error" boxes.
- Intentional overdose: Enter the drug name and "intentional overdose" as the event term. Check the "Intentional overdose" box. If drug abuse is suspected, check the "Drug abuse" box. If drug abuse is not suspected, check the "Drug misuse" box.
- Medication error that does not qualify as an overdose: Enter the name of the drug administered and a description of the error (e.g., wrong dose administered, wrong dosing schedule, incorrect route of administration, wrong drug, expired drug administered) as the event term. Check the "Medication error" box.
- Medication error that qualifies as an overdose: Enter the drug name and "accidental overdose" as the event term. Check the "Accidental overdose" and "Medication error" boxes. Enter a description of the error in the additional case details.
- Intercepted medication error: Enter the drug name and "intercepted medication error" as the event term. Check the "Medication error" box. Enter a description of the error in the additional case details.
- Drug abuse that does not qualify as an overdose: Enter the drug name and "drug abuse" as the event term. Check the "Drug abuse" box.
- Drug abuse that qualifies as an overdose: Enter the drug name and "intentional overdose" as the event term. Check the "Intentional overdose" and "Drug abuse" boxes.
- Drug misuse that does not qualify as an overdose: Enter the drug name and "drug misuse" as the event term. Check the "Drug misuse" box.
- Drug misuse that qualifies as an overdose: Enter the drug name and "intentional overdose" as the event term. Check the "Intentional overdose" and "Drug misuse" boxes.
- Drug administered to someone other than the patient: Enter the drug name and "patient supplied drug to third party" as the event term. Check the "Drug misuse" box.

As an example, an accidental overdose that resulted in a headache would require two entries on the Adverse Event eCRF, one entry to report the accidental overdose and one entry to report the headache. The "Accidental overdose" and "Medication error" boxes would need to be checked for both entries.

5.3.5.12 Patient-Reported Outcome Data

Adverse event reports will not be derived from PRO data by the Sponsor. Sites are not expected to review the PRO data for adverse events.

5.4 IMMEDIATE REPORTING REQUIREMENTS FROM INVESTIGATOR TO SPONSOR

Certain events require immediate reporting to allow the Sponsor to take appropriate measures to address potential new risks in a clinical trial. The investigator must report such events to the Sponsor immediately; under no circumstances should reporting take place more than 24 hours after the investigator learns of the event. The following is a list of events that the investigator must report to the Sponsor within 24 hours after learning of the event, regardless of relationship to study drug:

- Serious adverse events (defined in Section 5.2.2; see Section 5.4.2 for details on reporting requirements)
- Adverse events of special interest (defined in Section 5.2.3; see Section 5.4.2 for details on reporting requirements)
- Pregnancies (see Section 5.4.3 for details on reporting requirements)

For serious adverse events and adverse events of special interest, the investigator must report new significant follow-up information to the Sponsor immediately (i.e., no more than 24 hours after becoming aware of the information). New significant information includes the following:

- New signs or symptoms or a change in the diagnosis
- Significant new diagnostic test results
- Change in causality based on new information
- Change in the event's outcome, including recovery
- Additional narrative information on the clinical course of the event

Investigators must also comply with local requirements for reporting serious adverse events to the local health authority and IRB/EC.

5.4.2 Reporting Requirements for Serious Adverse Events and Adverse Events of Special Interest

5.4.2.1 Events That Occur prior to Study Drug Initiation

After informed consent has been obtained but prior to initiation of study drug, only serious adverse events caused by a protocol-mandated intervention should be reported. The paper Clinical Trial Serious Adverse Event/Adverse Event of Special Interest Reporting Form provided to investigators should be completed and submitted to the Sponsor or its designee immediately (i.e., no more than 24 hours after learning of the event), either by faxing or by scanning and emailing the form using the fax number or email address provided to investigators.

5.4.2.2 Events That Occur after Study Drug Initiation

After initiation of study drug, serious adverse events and adverse events of special interest will be reported until 28 days after the final dose of study drug. Investigators should record all case details that can be gathered immediately (i.e., within 24 hours after learning of the event) on the Adverse Event eCRF and submit the report via the electronic data capture (EDC) system. A report will be generated and sent to Roche Safety Risk Management by the EDC system.

In the event that the EDC system is unavailable, the paper Clinical Trial Serious Adverse Event/Adverse Event of Special Interest Reporting Form provided to investigators should be completed and submitted to the Sponsor or its designee immediately (i.e., no more than 24 hours after learning of the event), either by faxing or by scanning and emailing the form using the fax number or email address provided to investigators. Once the EDC system is available, all information will need to be entered and submitted via the EDC system.

Instructions for reporting serious adverse events that occur > 28 days after the final dose of study treatment are provided in Section [5.6](#).

5.4.3 Reporting Requirements for Pregnancies

5.4.3.1 Pregnancies in Female Patients

Female patients of childbearing potential will be instructed through the Informed Consent Form to immediately inform the investigator if they become pregnant during the study or within 30 days after the final dose of study drug. A paper Clinical Trial Pregnancy Reporting Form should be completed and submitted to the Sponsor or its designee immediately (i.e., no more than 24 hours after learning of the pregnancy), either by

faxing or by scanning and emailing the form using the fax number or email address provided to investigators. Pregnancy should not be recorded on the Adverse Event eCRF. The investigator should discontinue study drug and counsel the patient, discussing the risks of the pregnancy and the possible effects on the fetus. Monitoring of the patient should continue until conclusion of the pregnancy. Any serious adverse events associated with the pregnancy (e.g., an event in the fetus, an event in the mother during or after the pregnancy, or a congenital anomaly/birth defect in the child) should be reported on the Adverse Event eCRF. In addition, the investigator will submit a Clinical Trial Pregnancy Reporting Form when updated information on the course and outcome of the pregnancy becomes available.

5.4.3.2 Abortions

A spontaneous abortion should be classified as a serious adverse event (as the Sponsor considers abortions to be medically significant), recorded on the Adverse Event eCRF, and reported to the Sponsor immediately (i.e., no more than 24 hours after learning of the event; see Section [5.4.2](#)).

If a therapeutic or elective abortion was performed because of an underlying maternal or embryofetal toxicity, the toxicity should be classified as a serious adverse event, recorded on the Adverse Event eCRF, and reported to the Sponsor immediately (i.e., no more than 24 hours after learning of the event; see Section [5.4.2](#)). A therapeutic or elective abortion performed for reasons other than an underlying maternal or embryofetal toxicity is not considered an adverse event.

All abortions should be reported as pregnancy outcomes on the paper Clinical Trial Pregnancy Reporting Form.

5.4.3.3 Congenital Anomalies/Birth Defects

Any congenital anomaly/birth defect in a child born to a female patient exposed to study drug should be classified as a serious adverse event, recorded on the Adverse Event eCRF, and reported to the Sponsor immediately (i.e., no more than 24 hours after learning of the event; see Section [5.4.2](#)).

5.5 FOLLOW-UP OF PATIENTS AFTER ADVERSE EVENTS

5.5.1 Investigator Follow-Up

The investigator should follow each adverse event until the event has resolved to baseline grade or better, the event is assessed as stable by the investigator, the patient is lost to follow-up, or the patient withdraws consent. Every effort should be made to follow all serious adverse events considered to be related to study treatment or trial-related procedures until a final outcome can be reported.

During the adverse event reporting period (defined in Section [5.3.1](#)), resolution of adverse events (with dates) should be documented on the Adverse Event eCRF and in the patient's medical record to facilitate source data verification.

All pregnancies reported during the study should be followed until pregnancy outcome.

5.5.2 Sponsor Follow-Up

For serious adverse events, adverse events of special interest, and pregnancies, the Sponsor or a designee may follow up by telephone, fax, email, and/or a monitoring visit to obtain additional case details and outcome information (e.g., from hospital discharge summaries, consultant reports, autopsy reports) in order to perform an independent medical assessment of the reported case.

5.6 ADVERSE EVENTS THAT OCCUR AFTER THE ADVERSE EVENT REPORTING PERIOD

The Sponsor should be notified if the investigator becomes aware of any serious adverse event that occurs after the end of the adverse event reporting period (defined as 28 days after the final dose of study drug), if the event is believed to be related to prior exposure to study drug. These events should be reported through use of the Adverse Event eCRF. However, if the EDC system is not available, the investigator should report these events directly to the Sponsor or its designee, either by faxing or by scanning and emailing the paper Clinical Trial Serious Adverse Event/Adverse Event of Special Interest Reporting Form using the fax number or email address provided to investigators.

5.7 EXPEDITED REPORTING TO HEALTH AUTHORITIES, INVESTIGATORS, INSTITUTIONAL REVIEW BOARDS, AND ETHICS COMMITTEES

The Sponsor will promptly evaluate all serious adverse events and adverse events of special interest against cumulative product experience to identify and expeditiously communicate possible new safety findings to investigators, IRBs, ECs, and applicable health authorities based on applicable legislation.

To determine reporting requirements for single adverse event cases, the Sponsor will assess the expectedness of these events through use of the reference safety information in the document listed below:

Drug	Document
AT-527	AT-527 Investigator's Brochure

The Sponsor will compare the severity of each event and the cumulative event frequency reported for the study with the severity and frequency reported in the applicable reference document.

Reporting requirements will also be based on the investigator's assessment of causality and seriousness, with allowance for upgrading by the Sponsor as needed.

An aggregate report of any clinically relevant imbalances that do not favor the test product will be submitted to health authorities.

6. STATISTICAL CONSIDERATIONS AND ANALYSIS PLAN

All primary and secondary virology and efficacy outcomes will be analyzed in the modified intent-to-treat infected (mITTi) population. The mITTi population is defined as all patients randomized in the study who received any amount of study drug and had at least one positive SARS-CoV-2 RT-PCR test result *above or equal to the limit of quantification (LOQ)* during the study, with patients grouped according to the treatment assignment at randomization.

Safety analyses will be performed on the safety evaluable population, which consists of all patients who receive any amount of study drug. In all safety analyses, patients will be grouped according to the treatment that the patients actually received rather than the treatment assigned at randomization.

For *Cohorts A–D*, the primary virology analysis will be performed as part of a Day 10 review (accompanied with key safety review if deemed necessary, further details will be included in the SAP) which is to be completed after all patients enrolled in the current cohort have completed assessments through Day 10. Other endpoints will be analyzed at the completion of each full cohort or at the completion of the study.

For *Cohorts A–D*, all analyses at the Day 10 review or at the completion of each cohort will compare each AT-527 dose group and a combined placebo group, including all placebo patients enrolled across cohorts up to the cohort being analyzed, while analyses performed at the completion of the study will compare each AT-527 dose group and a combined placebo group from *Cohorts A–D*.

For *Cohort E*, the primary virology analysis will be performed as part of a Day 14 review (accompanied with key safety review if deemed necessary, further details will be included in the SAP) which is to be completed after all patients in *Cohort E* have completed assessments through Day 14. Other endpoints will be analyzed at the completion of the cohort.

For *Cohort E*, all analyses will compare the AT-527 dose group and the placebo group from *Cohort E* only. Data from cohorts with the same dose may be pooled to further evaluate the primary endpoint as part of a sensitivity analysis. Full details of all planned tables, listings, graphs, and statistical methods will be provided in a Statistical Analysis Plan (SAP), which will be finalized prior to the end of the study.

6.1 DETERMINATION OF SAMPLE SIZE

The primary objective of this study is to evaluate the antiviral activity of AT-527 compared with placebo. Approximately 60 patients will be randomized in a 1:1 ratio in Cohort A to receive AT-527 or placebo. Cohorts B–D will enroll approximately 40 patients in a 3:1 ratio to receive AT-527 or placebo, respectively. *Cohort E will enroll approximately 224 patients in a 1:1 ratio to receive AT-527 or placebo.*

The sample size for Cohort A–D is based on the primary endpoint of change from baseline in SARS-CoV-2 virus RNA measured by RT-PCR at a single timepoint. A sample size of 27 patients per arm (active or placebo) in the mITTi population will result in at least 80% power to detect a mean reduction in change from baseline of between 0.7 and 1.1 log₁₀ copies using a two-sample t-test for comparison of means, assuming a standard deviation of between 1.2 and 1.85 (Regeneron 2020) and based on a 1-sided 10% alpha. The sample size has been adjusted to 30 patients per arm to account for an estimated 90% SARS-CoV-2 positive rate and is based on a single-cohort comparison of AT-527 versus placebo.

For Cohort E, a sample size of 100 patients per arm (active or placebo) in the mITTi population will result in at least 80% power to detect a mean reduction in change from baseline of 0.5 log₁₀ copies using a two-sample t-test for comparison of means, assuming a standard deviation of 1.25 (deemed appropriate based on current data from WV43042) and based on a 1-sided 2.5% alpha. The sample size for Cohort E has been adjusted to 112 patients per arm to account for an estimated 90% SARS-CoV-2 positive rate. Based on emerging external data on direct acting antivirals in COVID-19 (Fischer et al 2021), a lower mean reduction in change from baseline of 0.5 log₁₀ copies has been utilized in Cohort E. A lower alpha level has also been selected to reduce the likelihood of a false positive result and enable a more robust evaluation of the antiviral activity of AT-527 at the selected dose regimen. This sample size also allows for a better characterization of the secondary endpoints.

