3. SAMPLE SIZE DETERMINATION

The primary objective of this study is to evaluate the antiviral activity of AT-527 compared with placebo. Approximately 60 patients will be randomized in a 1:1 ratio in Cohort A to receive AT-527 or placebo. Each additional cohort will enroll approximately 40 patients in a 3:1 ratio to receive AT-527 or placebo, respectively.

The sample size is based on the primary endpoint of change from baseline in SARS-CoV-2 virus RNA measured by RT-PCR at a single timepoint. A sample size of

27 patients per treatment group (active or placebo) in the modified intent-to-treat infected (mITTi; defined in [Table 2](#)) population will result in at least 80% power to detect a mean reduction in change from baseline of between 0.7 and 1.1 log₁₀ copies using a two-sample t-test for comparison of means, assuming a standard deviation of between 1.2 and 1.85 (Regeneron 2020) and based on a 1-sided 10% alpha. The sample size has been adjusted to 30 patients per treatment group to account for an estimated 90% SARS-CoV-2 positive rate and is based on a single-cohort comparison of AT-527 versus placebo.

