5.3.2 Main Analytical Approach for Primary Virology Endpoint

The primary virology endpoint analyses will be performed on the mITTi population using the nasopharyngeal swab data.

For each cohort, the change from baseline in the amount of SARS-CoV-2 virus RNA will be compared between the AT-527 group and the pooled placebo group (meaning all placebo patients up to and including the cohort being analyzed will be used to form the placebo comparator group) at Days 3, 5, and 7 using analysis of covariance (ANCOVA) with baseline viral load as a covariate.

The least squares mean (LSM) change and its standard error (SE) of means in each group, the difference between two groups in LSM change, SE, and 80% CI, and p-values will be presented. The LSM change will be presented graphically over time.

Additionally, descriptive summaries for the change from baseline will also be presented by treatment group. The change from baseline and the amount of SARS-CoV-2 virus RNA will also be presented graphically over time.

Baseline is defined as the Day 1 (pre-dose) nasopharyngeal swab ([Table 4](#)).

If the data are not normally distributed, a non-parametric alternative method will be used (e.g., Mann-Whitney U test) to compare distributions.

The qualitative result of the SARS-CoV-2 RT-PCR test is determined using cycle threshold (Ct) values. If the qualitative result is positive, then an associated quantitative result is also provided. The quantitative result is either numerical or below the limit of quantification (BLQ). The limit of quantification (LOQ) for the virus RNA is 120 copies/ml. If the virus RNA sample has a positive qualitative result, but a quantitative result BLQ, virus RNA will be imputed as LOQ – 1 (119 copies/mL). Negative qualitative samples will be imputed as LOQ/2 (60 copies/ml) before being transformed to the log10 scale. Samples reported as positive, but not quantifiable, will contribute to qualitative summaries, but will be treated as missing (not imputed) for quantitative summaries.

Missing data will not be imputed. Any missing data will not be included in the analyses.

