5.3.3 Sensitivity Analyses for Primary Virology Endpoint

A sensitivity analysis may be performed, whereby only data obtained at the nominal timepoint is used. This means that the time windows in [Table 4](#) would not be applicable; only samples collected on the scheduled timepoints (Days 3, 5, and 7) would be included in the analysis.

At the end of the study, sensitivity analyses will also be performed for each cohort with a combined placebo group from all cohorts.

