5.7 OTHER ANALYSES

5.7.1 Day 10 Review

The Day 10 analysis will include the primary virology analysis (nasopharyngeal swab) for each cohort, together with any sensitivity, supplementary, and subgroup (if data are available) analysis as described in Section 5.3. For Cohorts B-E, if the data are available in a timely manner, the change from baseline using saliva samples will also be summarized descriptively and plotted over time.

For all cohorts, if the data are available in a timely manner, the change from baseline in SARS-CoV-2 virus titer (Section 5.5) will also be described.

Demographic (including, but not limited to, age, sex and BMI) will be summarized as described in Section 5.7.3. A summary will be presented by treatment group (including a pooled placebo group up to the cohort being analyzed) and will be presented for the mITTi population and may, in addition, be presented for the safety population.

In addition, summaries of the placebo groups from each individual cohort up to the cohort being analyzed may be presented.

If deemed necessary, the following key safety data will be provided for the current AT-527 group and a pooled placebo group up to the cohort being analyzed:

- All AEs
- Serious AEs
- AEs leading to death
- Laboratory abnormalities

In order to avoid the risk of unblinding at patient level by the analysis of individual safety data, safety representatives independent to the study will be delegated to review any safety listings.

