5.7.3 Summaries of Demographics and Baseline Characteristics

Demographic and baseline characteristics (including, but not limited to, age, sex, BMI, self-reported race/ethnicity, onset of symptoms, baseline symptom severity, presence of underlying conditions, and pre-existing symptoms) will be summarized using means, SDs, medians, and ranges for continuous variables and proportions for categorical variables, as appropriate. A summary will be presented by treatment group (including a pooled placebo group) and will be presented for the mITTi population and may, in addition, be presented for the safety population.

In addition, summaries of the placebo groups from each individual cohort will be presented to allow for a high-level comparison of the patients to be pooled.

Medical history data, including surgery and procedures, and baseline conditions, will be listed using the safety population. Previous and concomitant treatments will be summarized descriptively by treatment group. Listings will also be provided.

In addition, there will be a summary and listing of all treatments with the indication given as 'COVID-19'.

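### The 27-per-arm single-cohort sizing stated for Cohorts A–D fits only Cohort A; Cohorts B–D rely on placebo from earlier cohorts, and no within-cohort estimate is required to check that

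*Protocol*

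**What the plan says.** Protocol 6.1 states that the sample size for Cohorts A–D comes from 27 mITTi patients per arm, a one-sided 10% alpha and a two-sample t-test, for differences of 0.7 to 1.1 log10 copies with SDs of 1.2 to 1.85. It inflates 27 to 30 per arm for a 90% positive rate and adds that the figure "is based on a single-cohort comparison of AT-527 versus placebo".

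The same section says: "Cohorts B–D will enroll approximately 40 patients in a 3:1 ratio to receive AT-527 or placebo, respectively". SAP Section 3 has the same sizing text and the same allocation: "Each additional cohort will enroll approximately 40 patients in a 3:1 ratio to receive AT-527 or placebo, respectively".

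The comparator is set elsewhere. Protocol Section 6 compares each Cohort A–D dose group with a combined placebo group, "including all placebo patients enrolled across cohorts up to the cohort being analyzed". SAP 5.3.2 agrees: "all placebo patients up to and including the cohort being analyzed will be used to form the placebo comparator group". The ANCOVA in Protocol 6.4.1 and SAP 5.3.2 adjusts for baseline viral RNA only.

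Three provisions bear on whether pooling is sound:

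- SAP 5.3.3, at the end of the study: "sensitivity analyses will also be performed for each cohort with a combined placebo group from all cohorts".
- SAP 5.7.3, within demographics and baseline characteristics: "summaries of the placebo groups from each individual cohort will be presented to allow for a high-level comparison of the patients to be pooled".
- SAP 5.7.1, at the Day 10 review, where the primary analysis is done: "summaries of the placebo groups from each individual cohort up to the cohort being analyzed may be presented".

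For Cohort E, Protocol 6.4.1 uses that cohort's own placebo patients only.

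**The concern.** The sample-size sections describe one comparison and the analysis sections run another. A reader of Protocol 6.1 or SAP Section 3 alone would credit each dose cohort with 80% power against its own randomised placebo. Cohorts B–D do not have that, and neither sizing section mentions pooling or the assumption it needs.

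That assumption matters here. Protocol 3.3.3 justifies placebo on the ground that viral load falls anyway in a generally self-limiting infection. Cohorts enrol sequentially (Protocol 3.1) over about 12 months (Protocol 3.2), and Protocol 1.1 describes emerging variants and breakthrough infections over the same period. If the natural decline differs between cohorts after adjustment for baseline viral RNA, the difference goes straight into the B–D dose estimates, because the model has no cohort or period term.

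The planned checks do not address this directly. The required by-cohort placebo summaries cover baseline characteristics, not viral-load change. The one sensitivity analysis on the comparator adds more pooled placebo.

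**Working it through.** **Inputs.** From Protocol 6.1: one-sided alpha 0.10; effect/SD pairs 0.7/1.2 and 1.1/1.85 (the ranges read low with low and high with high); 90% positive rate. Cohort A: 60 × 1/2 × 0.9 = 27 per arm. Each of B–D: 40 × 3/4 × 0.9 = 27 active and 40 × 1/4 × 0.9 = 9 placebo. From Protocol Section 6 and SAP 5.3.2: placebo accumulates, so the pool is 27 + 9 = 36 at B, 45 at C and 54 at D if cohorts run in order and fill.

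**Method.** Power = P(T > t(0.90, df)), with T noncentral t, noncentrality = effect / [SD × √(1/n₁ + 1/n₂)] and df = n₁ + n₂ − 2.

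**The plan's own figure.** At 27 v 27 with 0.7/1.2, the SE is 1.2 × √(2/27) = 0.327, noncentrality 2.143 and power 80.1%. With 1.1/1.85, power is 81.2%. And 27/0.9 = 30. The stated figures reproduce.

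**Cohorts B–D.**

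| Comparison | Active v placebo | Power, 0.7/1.2 | Power, 1.1/1.85 |
|---|---|---|---|
| Own cohort | 27 v 9 | 58.5% | 59.7% |
| Own cohort, all evaluable | 30 v 10 | 61.7% | 62.9% |
| Pooled, Cohort B | 27 v 36 | 84.0% | 85.0% |
| Pooled, Cohort C | 27 v 45 | 86.4% | 87.4% |
| Pooled, Cohort D | 27 v 54 | 88.1% | 89.0% |

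**Share of the pool from earlier cohorts.** 27/36 = 75% (B), 36/45 = 80% (C), 45/54 = 83% (D). These are upper bounds on the non-concurrent share, because cohorts may overlap.

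**Effect of a shift.** The documents give no size for a shift, so the values below are assumptions, meaning what is left after baseline adjustment. Bias = share × shift. At Cohort B with a shift of 0.2, bias = 0.75 × 0.2 = 0.15 log10.

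- *Earlier placebo falls less than own-cohort placebo (favours AT-527).* One-sided error, nominally 10%, over B–D: a shift of 0.2 gives 21.4–24.3% (SD 1.2) or 16.7–18.4% (SD 1.85); a shift of 0.5 gives 47.5–57.3% or 31.2–37.0%.
- *Same shifts, earlier-cohort share halved for overlap.* 0.2 to 0.5 gives about 15–29% (SD 1.2) or 13–21% (SD 1.85).
- *Shift in the other direction.* Power at (effect − bias), for shifts of 0.2, 0.3 and 0.5: 69–72%, 60–62% and 39–41% (0.7/1.2); 77–80%, 71–75% and 60–61% (1.1/1.85). Power reaches 80% at an adverse shift of 0.06–0.12 log10 (0.7/1.2) or 0.12–0.20 (1.1/1.85).

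**Precision of an own-cohort estimate.** 80% CI half-width = t(0.90, df) × SD × √(1/27 + 1/n placebo). At 27 v 9 this is 1.307 × 1.2 × √(1/27 + 1/9) = 0.60 log10, or 0.93 with SD 1.85. Pooled, it is 0.37–0.40 or 0.56–0.61.

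**The case against.** The planned B–D test is not underpowered if the placebo groups are exchangeable: each cohort has its 27 evaluable active patients, the pool has at least 36 placebo patients, and 84–89% exceeds the claimed 80%. The 59% belongs to a test nobody plans. Pooling is disclosed in Protocol Section 6, just before 6.1, and the 3:1 allocation is given in 6.1 itself. All of this stands, and the point is not that the planned test lacks power. It does not make the sizing statement correct for B–D or supply the missing condition.

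Some indirect checks exist. Cohort placebo means could be recovered by subtracting successive pooled summaries if the analysed patients stay the same, and the end-of-study analysis in SAP 5.3.3 sets Cohort A's own placebo beside the full pool. Neither is a required within-cohort estimate with a CI for B–D.

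The own-cohort estimate is also weak as a diagnostic. The SE of own minus earlier placebo is SD × √(1/9 + 1/n earlier) = 0.44–0.46 (SD 1.2) or 0.68–0.71 (SD 1.85), so shifts of 0.2–0.5 would often go unseen. The pooled estimate has the smaller mean squared error until the shift exceeds those same values. This is a good reason to keep pooling as the primary analysis and to place the own-cohort result beside it.

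Finally, the shift sizes are assumed. The 57% is an extreme corner (Cohort D, SD 1.2, the full 83% share, 0.5 log10), and the study is described as hypothesis-generating, with Cohort E judged against its own placebo. These limit the consequence.

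**Conclusion.** The concern holds. The 27-per-arm arithmetic is right, but among Cohorts A–D it describes Cohort A alone. Cohorts B–D have about 59–63% power within cohort, and 84–89% with cumulative placebo on condition that placebo response is stable across cohorts. Neither sample-size section states that condition, and no required within-cohort treatment estimate tests it. The power figures rest on the plan's effect/SD pairs, full enrolment in order and a 90% positive rate. The error-rate figures rest on assumed shifts and on upper-bound shares of earlier placebo, so they illustrate sensitivity and do not predict bias. The correction should be made, but it does not undermine the design: pooling can remain the primary analysis.

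**What to change.** 1. In Protocol 6.1 and SAP Section 3, confine the 27-per-arm single-cohort basis to Cohort A. For Cohorts B–D, state that the comparison uses cumulative pooled placebo, with 84–89% power assuming no shift in placebo response between cohorts, and about 59–63% power within cohort.
2. In SAP 5.3.3, require for Cohorts B–D the same ANCOVA against own-cohort placebo only, with the estimate and 80% CI at Days 3, 5 and 7, shown beside the pooled result. This is the unpooled approach the protocol already uses for Cohort E.

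The cost is wording in two sections and one extra table from data already collected. The sponsor must accept a less favourable within-cohort power figure and a wide own-cohort interval (half-width about 0.60 to 0.93 log10), which should be labelled as a check on pooling and not as a second test. No patients, samples or visits are added.
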